- e. The methods described in the paper by Schmuck and Carey (2010) will be used for the transverse microradiography (TMR) of the samples in this study. The extracted teeth will be sectioned and digital images will be taken with incident and transmitted polarized light to visualize any lesion in the sample. TMR will be used to determine surface lost. TMR determination of lesion depth will be used to compare the measurement via polarized light microscopy.

IV. Research Methods:

- a. **Outcome Measures:** mineral density profile and lesion depth of extracted teeth in these experiments. Mineral density will be measured by transverse x-ray microradiography (Schmuck and Carey, 2010), lesion depth will be measured by polarized light microscopy (Wefel and Harless, 1984; Darvishiabyaneh and Carey 2016; and for orthodontic evaluations Lee *et al.*, 2015).

- b. **Description of Population to be Enrolled:**

Research participants will be between 12 and 89 years of age who are subjects undergoing orthodontic treatment at the Department of Orthodontics Clinic, School of Dental Medicine, University of Colorado. The following inclusion criteria will be applied: comprehensive fixed orthodontic treatment with brackets from at least second premolar to second premolar, treatment planned already for the extraction of at least 3 bicuspids (any combination), patient at the University of Colorado School of Dental Medicine Orthodontic Clinic, can place bracket base on teeth to be extracted for at least 1 month

prior to extractions, no previous white spot lesions, caries or restorations present on the facial surface of the teeth being studied, adequate oral hygiene.

In the recruitment process the attending resident will provide information and answer any questions about the study to the potential study participant. If there is interest on behalf of the patient then the consent form will be reviewed and after presentation the form will be signed by all who wish to join the study. The consent form is attached as a separate document. There is no benefit to the patient to participate other than participating in a study that may find a beneficial treatment for others in the future. There will be no effect on the patients treatment or experience should they decide not to participate or to participate.

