(experimental group). The number of patients required for this study was calculated from studies that had a similar design (de Moura *et al.*, 2006; Uysal *et al.*, 2010). De Moura *et al.* studied the effect of a fluoridated antiplaque dentifrice on the development of caries lesions adjacent to orthodontic brackets. Fourteen orthodontic patients with planned extractions were divided into two groups of 7. The patients used experimental or control toothpastes 3 times per day for 28 days. The teeth were extracted and the mineral loss was determined in the cross-sections by use of microhardness. The results showed that there was a statistically significant ($p < 0.05$) improvement with the experimental antiplaque toothpaste for the first 10 μm of depth. There was no significant difference at deeper distances from the surface. A calculation of their experimental power shows that an n of 7 per group is insufficient to achieve 80 % power at an α of 0.05. Additionally, the microhardness method is less sensitive to mineral density loss than the TMR methods to be used in this study. Balancing the increased sensitivity via TMR with the insufficient power in the de Moura study to make conclusions about the efficacy of the antiplaque toothpaste to prevent tooth loss; we opt to be more conservative and use a larger n per group. Based on the previously observed variations in mineral density and clinically relevant minimum difference of 10 % mineral density in the first 50 microns of tooth surface between the negative control and the experimental K18-UDMA sealant, the number of subjects to achieve 80 % power at an alpha of 0.05 is 20 subjects. It is anticipated that up to 30 patients may be recruited to this study, with 20 needed for statistical power to answer our research question.

2. If the patient has a fourth bicuspid is planned for extraction, a random treatment will administered to this last tooth. This will provide additional information on the effect of location (upper or lower jaw) on the protective ability of the experimental sealant.

- ii. Teeth planned for extraction will be bonded with a bracket pad using one of three systems: no treatment (negative control), UDMA sealant (control) and K18-UDMA sealant (experimental group). The bracket pad does not have the bracket protruding from the base.
 - 1. Blinding:

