5. The use of smooth sealants on the teeth to be extracted is not unique as many patients have a smooth surface sealant placed after the orthodontic brackets are placed. There are several commercial products that release fluoride specifically for the purpose of prevention of WSL. It is unfortunate that there are few well designed studies about the use of these sealants.
6. Should the patient decide to withdraw from planned orthodontic therapy prior to extractions, the bracket pads can be removed following the standard procedures for removing brackets at the same time as the brackets are removed. The sealants will come off at the same time because the standard procedure includes polishing the tooth surfaces when brackets are removed.
7. Patient identification is only to identify which tooth received the specific treatments so that when the teeth are extracted by the oral surgeon the groups can be identified. No patient information is associated with the outcome measures.

- ii. Justification of Procedures: There are no procedures delivered to the patient that are not within the scope of the standard procedures for orthodontic patients. All data is gathered from the extracted teeth in the laboratory.
 - iii. Data Collection Tools: Mineral density and lesion depth will be determined in the laboratory through histological examination of the teeth. Briefly, the teeth are cross-sectioned through the bracket pad to generate a 1 mm thick slab from the middle of the tooth. This slab is observed under polarized light microscopy to measure the lesion depth (if any) from the surface, and subjected to x-ray to determine the mineral density across the lesion.
- e. **Potential Scientific Problems**: None are anticipated.
- f. **Data Analysis Plan**
- i. Statistical analysis will include graphical evaluations, along with descriptive statistics (mean, standard deviation), and one-way ANOVA for the three groups for both mineral density and lesion depth outcomes. If appropriate, there will be follow-up ranked comparison testing at a significance of $P \leq 0.05$. There will be paired-t tests between UDMA and negative controls, UDMA-K18 and negative controls, and paired-t tests between UDMA and UDMA-K18 sealants on mineral density and lesion depth outcomes. Should there be data from a 4th tooth (2 teeth will receive the same treatment) the data from the 2 teeth with the same treatment will be averaged prior to comparison to the controls.

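### The region that gives the tested mineral density value is undefined, and the laboratory text (read across the lesion) conflicts with the fixed 50-micron window used for the sample size

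*Combined protocol and SAP*

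**What the plan says.** Four places in the combined protocol and SAP bear on the density endpoint.

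- **Outcome Measures (IV.a)** names "mineral density profile and lesion depth of extracted teeth in these experiments". It gives no depth range for the profile and no summary value.
- **Sample size (IV.c.i.1)** rests on a "clinically relevant minimum difference of 10 % mineral density in the first 50 microns of tooth surface", K18-UDMA against the negative control, and concludes that "the number of subjects to achieve 80 % power at an alpha of 0.05 is 20 subjects". The SD is only alluded to ("Based on the previously observed variations in mineral density").
- **Data Collection Tools (IV.d.iii)** has the slab viewed under polarized light "to measure the lesion depth (if any) from the surface" and then "subjected to x-ray to determine the mineral density across the lesion".
- **Data Analysis Plan (IV.f.i)** applies one-way ANOVA and three paired t-tests to mineral density and to lesion depth. It names no depth window and no rule for a tooth without a lesion.

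The 50-micron window appears only in the sample-size text.

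**The concern.** A paired t-test needs one number per tooth. The documents point to two regions for that number: a fixed outer 50 microns in the sizing, and the lesion itself in the laboratory text. These are different endpoints.

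If the lesion sets the window, the window is part of the outcome: wide on a damaged tooth, narrow on a protected one. A tooth with no lesion has nothing to read across. Such teeth are to be expected. Studied surfaces must be free of white spot lesions at entry (IV.b), exposure is about 30 days (IV.d.i), the sealant is meant to prevent demineralization (Section I), and IV.d.iii itself allows for a tooth without a lesion. They would include the sealant's best results, and without a density value their pairs could leave the paired comparison.

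At stake is whether the density test addresses the difference for which 20 patients were judged sufficient.

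**Working it through.** **Step 1: the plan's own figure.** N = 20 cannot be reproduced, because no SD is given. Taking the 10 % as 10 percentage points, the SD that 20 subjects and 80 % power at alpha 0.05 imply is:

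| Method | Two-sided | One-sided |
|---|---|---|
| Paired t, 20 pairs (SD of differences) | 15.1 (10 / 0.66) | 17.3 |
| Two-sample t, 20 per group (SD) | 11.0 | 12.5 |

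The two-sided normal approximation gives 10 × √20 / (1.96 + 0.84) = 16.0 paired and 10 × √10 / (1.96 + 0.84) = 11.3 two-sample. Over a range of assumed SDs of paired differences, the pairs needed are: SD 10, 10 pairs; 12.5, 15; 15, 20; 17.5, 27; 20, 34. The steps below use 15.1, two-sided and paired, and hold it the same for both windows. That is an assumption.

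**Step 2: the two windows on the same teeth.** Let L be lesion depth (at most 50 microns) and m the mineral loss.

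- Uniform loss m: fixed-window mean = m × L / 50; lesion-window mean = m.
- Triangular loss, m at the surface falling to 0 at depth L: fixed-window mean = m × L / 100; lesion-window mean = m / 2.

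All profiles below are assumed. Each row gives control v K18-UDMA; power is for 20 pairs.

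| Loss m, depth L | Fixed 0-50 microns | Power | Lesion window | Power |
|---|---|---|---|---|
| Uniform, 20 v 20 %, 50 v 25 | 20 − 10 = 10 | 80 % | 20 − 20 = 0 | 5 % |
| Triangular, 40 v 40 %, 50 v 25 | 20 − 10 = 10 | 80 % | 20 − 20 = 0 | 5 % |
| Uniform, 30 v 30 %, 45 v 10 | 27 − 6 = 21 | above 99 % | 30 − 30 = 0 | 5 % |
| Triangular, 30 v 20 %, 50 v 25 | 15 − 5 = 10 | 80 % | 15 − 10 = 5 | 29 % |
| Uniform, 30 v 20 %, 50 v 25 | 30 − 10 = 20 | above 99 % | 30 − 20 = 10 | 80 % |
| Uniform, 30 v 10 %, 10 v 10 | 6 − 2 = 4 | below 29 % | 30 − 10 = 20 | above 99 % |

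The first three rows set the loss inside the lesion equal in both arms, and the lesion window then shows nothing. In rows four and five the sealant also lowers that loss, and the effect is halved. In the last row the lesions are equally shallow, and the order reverses.

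**Step 3: lesion-free teeth.** Assume the sealant fully protects half of the K18-UDMA teeth, and that the other half and all controls lose 20 % uniformly over 50 microns. In 20,000 simulated trials of 20 patients:

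- Fixed window on every tooth: difference 10 points, power about 64 %. This is below 80 % because the mixture widens the spread of differences.
- Lesion window: about 10 of 20 pairs remain, the difference is 0, and the test rejects in about 5 % of trials.

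**Step 4: lost pairs alone.** If the 10-point effect is kept but pairs drop out:

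| Share of pairs lost | From 20 patients | From 30 patients |
|---|---|---|
| 20 % | 16 pairs, 70 % | 24 pairs, 87 % |
| 30 % | 14 pairs, 63 % | 21 pairs, 82 % |
| 50 % | 10 pairs, 46 % | 15 pairs, 66 % |

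**The case against.** The strongest reply is that IV.d.iii was never meant as an analysis rule. It presents itself as a brief description. Section III.e says that a cited microradiography method will be followed and that it also measures surface loss. IV.a promises a profile, which could be averaged over the outer 50 microns on any tooth, and reading across a lesion may simply describe a scan running inward from the surface. IV.f.i excludes no tooth. All of this stands.

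A reader might therefore go too far in inferring that the plan prescribes a lesion-only mean, drops lesion-free teeth and is biased toward no difference. No section says so. What remains is that no section says the opposite: the fixed window stays in the sample-size paragraph, and the value to be tested is left open.

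Three further points limit the size:

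- Complete loss of the effect is a consequence of assuming equal loss inside lesions in both arms. The direction is not general either. Of the cited 28-day study, in which the gain was confined to the outer 10 microns, IV.c.i.1 says "There was no significant difference at deeper distances from the surface". If lesions here are that shallow, the fixed window may be the one that dilutes.
- Lesion depth is a separate outcome and would still show a depth effect, for example 45 v 10 microns in the third row of the table. This protects the trial's overall conclusion in part, but the sample size was not set on depth.
- The plan allows that "up to 30 patients may be recruited to this study, with 20 needed for statistical power". Full recruitment absorbs the loss of up to a third of pairs, but not half.

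A reader might also count the lack of a sound-enamel reference as an error. The cited method may include one, which cannot be checked here, and each patient already supplies an untreated control tooth.

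**Conclusion.** The concern holds as an undefined and internally inconsistent endpoint. The laboratory text and the sample-size text name different regions, and the outcome and analysis sections settle on neither. That finding rests on the wording alone and is secure.

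The consequence is conditional on IV.d.iii being followed literally. The density value then depends on the outcome, is missing for lesion-free teeth, and is not the quantity behind the 80 % power. Under the assumed profiles a 10-point effect can fall to 5 points (power 29 %) or to 0 (about 5 %), or it can survive. Which of these applies depends on lesion profiles and an SD that the documents do not give. It would be wrong to say that the trial will lose its effect. It is right to say that the point should be settled before any tooth is read.

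**What to change.** Use the same definition in IV.a, IV.d.iii and IV.f.i: *the tested density value is the mean mineral density over a fixed depth of 0-50 microns, at the same site on every tooth, whether or not a lesion is seen.* Two additions are needed:

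- State the surface reference from which depth 0 is measured, so that enamel already lost is counted. Section III.e expects surface loss, and a window starting at the residual surface would miss it.
- Score lesion depth as 0 when no lesion is seen.

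Optional and secondary: express density relative to deeper sound enamel on the same slab, and report the 0-10 micron band descriptively, without a further test.

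The cost is protocol wording and slightly more image reading per tooth; patients undergo nothing new. The one statistical downside is that a fixed 50-micron window may dilute an effect confined to very shallow lesions, which the descriptive 0-10 micron band would make visible.

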COMIRB Protocol

Version Date: 12-14-2017

COLORADO MULTIPLE INSTITUTIONAL REVIEW BOARD
 [name] [contact] [contact]

Project Title: Prevention of enamel demineralization in fixed appliance orthodontic patients using UDMA-K18 sealant to prevent microbial attachment. A randomized split mouth clinical trial.

Principal Investigator: [name], Professor and Director of Translational Research
Orthodontics Residents: [name] and [name]

[name] is the research mentor for University of Colorado, School of Dental Medicine, Department of Orthodontics residents Drs. [name] and [name]. Drs. [name] and [name] will be performing all the sealant and bracket placements. [name] will assist in the histology and evaluation of the extracted teeth.

- I. **Hypotheses and Specific Aims:** The hypothesis is that UDMA-K18 containing smooth surface sealant will be more effective at reducing enamel demineralization than the UDMA control or no treatment. This study will assess the effect of a quaternary ammonium methacrylate (QAM) called K18 antimicrobial compound tethered to urethane dimethacrylate resin (UDMA-K18). This resin will be tested against UDMA sealant and no sealant. This study will evaluate effectiveness of a UDMA-K18 sealant to prevent biofilm attachment to tooth surfaces thereby eliminating the possibility for the tooth to be demineralized.

- II. **Background and Significance:** Far too frequently orthodontic patients are unable to perform sufficient oral hygiene to remove all of the bacterial biofilm surrounding orthodontic brackets. When the bacterial biofilm is not removed, tooth demineralization is possible. The incidence of new tooth demineralization, often called white spot lesions (WSL), has been studied at the University of Colorado Department of Orthodontics. Forty-four orthodontic patients ages between 11 and 21 years of age were assessed over the course of their therapy for the development of new WSL. This study reported that 84.6 % of the patients developed new WSL, and the total area of WSLs also increased from $16.6 \pm 23.6 \text{ mm}^2$ per patient to $42.6 \pm 50.7 \text{ mm}^2$ per patient. The period of therapy where the greatest increase in WSL occurred was between initial banding and 1 year of therapy. The area most susceptible to WSLs during treatment is the cervical third, and both anterior and posterior teeth are equally susceptible to the development of new lesions. (Faranesh et al., 2017). Given that the bacterial biofilm is

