The requirement of at least 3 bicuspid teeth to be extracted is to meet the requirements of the matched pair experimental design. Because each patient is different and their oral biology is different treating and analyzing teeth that do not have matched pairs in the same patient are not useful for this study therefore the inclusion criteria cannot include patients with less than 3 planned extractions.

The inclusion of minors aged 12 and older is because minors are more likely to develop white spot lesions and should this sealant provide protection then the whole orthodontic population will benefit. Also there is no risk associated with the procedures outlined in this trial so there is no reason to exclude minors from this study.

Currently the Department of Orthodontics enrolls 50 to 75 patients per month. The number of patients that meet the above inclusion criteria will be about 30 % of those enrolled. It is anticipated that a minimum of 1 patients per month can reasonably be enrolled into the study. Thus, the study should receive full enrollment in 4 months.

c. Study Design and Research Methods (see CONSORT diagram on last page)

- i. The study has a split mouth clinical design where each of two controls and one experimental sealant will be in each person.
 1. Each patient will have all three experimental sealant systems including: no sealant (negative control), UDMA sealant (control) and K18-UDMA sealant

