- iv. When the patient reports to the oral surgeon for extractions, the extracted teeth will be placed in Tooth Storage Solution which is antimicrobial and does not alter the surfaces or composition of the teeth. The container will have the patient number and date of extraction written on the label.
- v. There is no difference related to the procedures used to extract the teeth that are to be extracted for orthodontic therapy. The standard of care is the same for all patients whether there is a sealant or not on the teeth to be extracted.
- vi. These teeth will be returned to the laboratory for histological evaluation of mineral density and lesion depth.
- vii. The original location of the extracted teeth can be easily made from the tooth morphology. The source of the extracted tooth (original location and patient number) will be recorded in the laboratory notebook, and when data evaluation is conducted will be used to identify the experimental group for that the tooth.

d. Description, Risks and Justification of Procedures and Data Collection Tools:

- i. Description: These experiments utilize bicuspid that are treatment planned for extraction to allow for an approximant 30-day period where the experimental treatment is exposed to the environment of the mouth in exactly the same manner as all other teeth in the patients mouth.

1. About 30 % of the patients who receive treatment planning for orthodontic therapy will require extraction of bicuspid.
2. The extractions are usually scheduled to occur at about 30 days after bracket bonding to the other teeth.
3. The experimental design requires that each patient will have all experimental and control conditions (on separate teeth). This split mouth paired samples design increases the power of the experiment and allows for fewer patients to be required for sufficient statistical power. Paired analyses within an individual renders greater sensitivity to experimental effects than population based analyses.
4. Bonding bracket pads instead of full brackets removes the protruding portion of the bracket so that it does not interfere with the orthodontic wires that are placed for the therapy.

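### The three-group test is written as a one-way ANOVA with no patient term although every patient receives all three treatments; as written it is conservative if teeth within a mouth are positively correlated, and no deciding test is named

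*Combined protocol and SAP*

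**What the plan says.** Section IV.c.i gives every patient all three conditions: "each of two controls and one experimental sealant will be in each person". Section IV.d.i.3 explains why: "Paired analyses within an individual renders greater sensitivity to experimental effects than population based analyses". Section IV.g.i again presents within-patient differences as the strength of the design.

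Section IV.f.i then lists three kinds of test and does not rank them:

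- a "one-way ANOVA for the three groups for both mineral density and lesion depth outcomes", with no patient, block or repeated-measures term;
- an unnamed follow-up procedure: "If appropriate, there will be follow-up ranked comparison testing at a significance of" P ≤ 0.05;
- paired t-tests for all three pairs on both outcomes, beginning: "There will be paired-t tests between UDMA and negative controls, UDMA-K18 and negative controls".

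Section IV.c.i.1 sizes the trial at 20 subjects for 80 % power at alpha 0.05, on a 10 % difference in mineral density "in the first 50 microns of tooth surface between the negative control and the experimental K18-UDMA sealant". The data analysis plan does not carry that contrast forward as the main one. The hypothesis in section I, that the K18 sealant "will be more effective at reducing enamel demineralization than the UDMA control or no treatment", does not settle which comparison decides.

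**The concern.** A one-way ANOVA treats the teeth as three independent groups. Here they are triplets from the same mouths, so differences between patients inflate the error term without affecting the treatment contrast. The design's main advantage is lost in the one test that looks at all three treatments together.

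The practical risk is disagreement between tests. The three-group test may be non-significant while the paired t-test on the contrast that sized the trial is significant. Some of that happens with a correct test too, but the missing patient term adds to it. Since no sentence says which test decides, the conclusion could be chosen after the data are seen.

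**Working it through.** **Inputs.** From the documents: three treatments per patient, n = 20 (up to 30 may be recruited), alpha 0.05, power 80 %, difference 10 (IV.c.i and IV.c.i.1). The documents give no SD, no within-mouth correlation and no sidedness. I assume two-sided tests and show correlations ρ of 0, 0.3, 0.5 and 0.7. The protocol's case for pairing implies that ρ is positive but gives no value.

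**The plan's own figure.** N = 20 cannot be reproduced without an SD, so I solved backwards with the noncentral t distribution for 80 % power.

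- Reading A, a paired test with n = 20: standardised difference 0.660, so the SD of differences is 10/0.660 = 15.1. The tooth SD is then 15.14/√(2(1−ρ)) = 12.8, 15.1 and 19.5 at ρ = 0.3, 0.5 and 0.7.
- Reading B, two independent groups of 20: standardised difference 0.909, so the tooth SD is 10/0.909 = 11.0.

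The documents do not say which was used.

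**Why the test is conservative.** Take equal tooth variance σ² and common correlation ρ. When the treatments are equal, the treatment mean square has expectation σ²(1−ρ). The one-way error mean square has expectation σ², and the patient-blocked error has σ²(1−ρ). So the one-way F is too small by a factor of about (1−ρ), while the blocked F is on the right scale.

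Hand check, with 2 and 3×20−3 = 57 degrees of freedom: P(F > x) = (1 + 2x/57)^(−28.5), and the 5 % point is 3.16. Replacing 3.16 by 3.16/(1−ρ):

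- ρ = 0.3: x = 4.51, P = 1.5 %
- ρ = 0.5: x = 6.32, P = 0.33 %
- ρ = 0.7: x = 10.53, P = 0.013 %

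This ignores the extra variability of the one-way error term under correlation, which matters only in the far tail. Simulation (tens of thousands of trials per setting) gives 1.5, 0.4 and 0.03 %.

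**Type I error at nominal 5 %, n = 20, simulated normal data.** The unequal SDs are an illustration taken from the in-vitro erosion study in section III.d, which reports 44.7 ± 21.9 µm for the negative control and 29.3 ± 9.6 µm for a sealant.

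| | ρ = 0 | 0.3 | 0.5 | 0.7 |
|---|---|---|---|---|
| Equal SDs, one-way | 5 % | 1.5 % | 0.4 % | 0.03 % |
| Equal SDs, blocked | 5 % | 5 % | 5 % | 5 % |
| SDs 21.9/9.6/9.6, one-way | 6.5 % | 3.7 % | 2.1 % | 1.1 % |

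With the unequal SDs, a blocked F without correction runs at 6.4 to 7.1 % across these correlations.

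**Power of the three-group test, n = 20, equal SDs, means 0/5/10.**

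| | ρ = 0.3 | 0.5 | 0.7 |
|---|---|---|---|
| A, one-way | 55 % | 35 % | 11 % |
| A, blocked | 72 % | 72 % | 72 % |
| B, one-way | 72 % | 73 % | 75 % |
| B, blocked | 84 % | 95 % | over 99 % |

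Under B the one-way power does not fall with correlation (71 % at ρ = 0), so the loss there is a gain forgone.

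**Disagreement, same settings.** Share of trials in which the UDMA-K18 versus negative control paired t-test is significant and the three-group test is not:

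- A: one-way 25, 45 and 69 %; blocked about 10 % throughout.
- B: one-way 19, 24 and 24 %; blocked 6, 3 and 0.2 %.

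At ρ = 0 about 9 % disagree with either test. Under B with 30 patients the excess due to the missing term is only 4 to 6 points.

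**Lesion depth.** Section IV.d.iii plans "to measure the lesion depth (if any) from the surface", so zeros are likely. With 30 to 70 % zeros and equal latent variances, one-way type I error is 1.8–2.1, 0.6–1.0 and 0.06–0.3 % at latent ρ = 0.3, 0.5 and 0.7, against 3.8–4.9 % blocked. Power was not simulated for this outcome.

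**Follow-up error term.** With SDs 21.9/9.6/9.6 and no treatment effect, pairwise tests on the pooled within-patient error reject about 9 % of the time against negative control and under 0.5 % for UDMA-K18 versus UDMA. The paired t-tests stay at about 5 %.

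**Multiplicity.** With all treatments equal, equal SDs and n = 20, at least one of the three unadjusted paired t-tests is significant in about 12.5 % of trials per outcome. Independent tests would give 1 − 0.95³ = 14.3 %.

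**The case against.** The strongest reply is that valid within-patient tests are already planned. Section IV.f.i has paired t-tests for every pair on both outcomes. The words about appropriateness attach only to the ranked comparison, so nothing makes the paired tests wait for the ANOVA. This stands, and it confines the damage to the three-group test and to follow-up that borrows its error term.

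Second, one-way may mean one factor, and a one-way repeated-measures ANOVA is standard. That is possible given sections IV.c.i, IV.d.i.3 and IV.g.i. If it is what was meant, the text should say so, and the same edit settles it.

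Third, the very small error rates assume equal SDs, and the in-vitro SDs in section III.d are far from equal. This also stands. It softens the figures, and it means that a patient block alone is not a complete remedy. Those data are only illustrative of what the trial will see.

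Fourth, the lack of a named deciding test would exist however the ANOVA were specified. I agree, so it is a secondary point here.

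A reader might infer that the trial is underpowered or that its 80 % claim is wrong. The documents do not support that: the claim concerns one pairwise contrast, a valid paired test of it is planned, and no SD is given against which to test the claim. A reader might also infer that the plan as a whole is conservative. It is not, because the unadjusted paired tests err in the other direction. Nor is the ANOVA conservative in every case: at zero correlation it is near nominal with equal SDs and slightly liberal (6.5 %) with the unequal SDs shown.

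**Conclusion.** The point holds in limited form and should be fixed. As written, the three-group test omits the patient term that the design calls for. With positive within-mouth correlation it has too low a type I error and less power than a blocked test. The direction holds in every positive-correlation setting in the tables above. The size does not come out as a single figure, because it depends on an SD and a correlation that the documents do not give. Depending on the reading of the sample size, the power shortfall runs from about 12 points (84 − 72, B at ρ = 0.3) to about 61 points (72 − 11, A at ρ = 0.7). These power figures rest on normal data, equal SDs, two-sided tests and UDMA midway between the other two treatments.

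**What to change.** In IV.f.i, replace the one-way ANOVA wording with:

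> Repeated-measures (randomised-block) ANOVA across the three treatments with patient as block and a Greenhouse-Geisser correction or, if a tooth is missing, a linear mixed model with treatment as fixed effect and patient as random effect.

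Replace the unnamed ranked comparison with the paired t-tests already planned, each using the error of its own pair and not the pooled within-patient error. The averaging of duplicate teeth can stay.

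Secondarily, add:

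> The deciding test is the paired t-test of UDMA-K18 versus negative control on mineral density in the first 50 microns, two-sided alpha 0.05. The three-group test, the other two pairs and lesion depth are secondary.

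This is the contrast on which section IV.c.i.1 sizes the trial, and a test that IV.f.i already contains. If the sponsor wants both comparators in the hypothesis to be decisive, state the rule: both must be significant at 0.05 (no adjustment needed), or either suffices (adjust, for example with Holm).

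Cost: a wording change and slightly more analysis work. No new data are needed, because section IV.c.vii already has patient number and tooth location recorded.
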